1045 **Statistical power of two-sided exact McNemar's test with 2.5% type 1 error, assuming a difference of 50% (25%**
1046 **vs. 75%) in hypoglycemia rate between two arms. Crossover design, N=20.**

Proportion discordant (higher value corresponds to lower correlation between two arms)	Proportion of those having hypoglycemia with glucagon	Statistical power
--	---	-------------------

	that do not have hypoglycemia when glucagon is withdrawn	
0.625†	25%	75%
0.6	20%	78%
0.575	15%	82%
0.55	10%	86%
0.525	5%	90%
0.505	1%	93%

1047 †corresponding to independence between two arms

1048

1049 **Power Calculation for Aim 2**

1050 No formal power analysis has been completed for the determination of a relationship between VOCs and
1051 hypoglycemia. Combining hypoglycemia that occurs during exercise and hypoglycemia that occurs after a
1052 correction bolus with a glucose target of 50 mg/dl, we expect to capture breath and sweat in at least 30 visits
1053 during which hypoglycemia (BG < 60 mg/dl) occurs. During visits in which hypoglycemia occurs, we will capture
1054 at least one set, and likely 2 or more sets, of samples of breath and sweat during hypoglycemia, and at least 4
1055 during normoglycemia in the same participants on the same day. This is anticipated to provide samples from 30-
1056 40 hypoglycemic episodes and paired samples during normoglycemia (both before and after hypoglycemia) from
1057 the same participants. If there is a robust correlation between a VOC marker and hypoglycemia, this should
1058 provide sufficient power to identify VOC markers of hypoglycemia.

1059

1060 **VII. Risks and Discomforts**

1061

1062 There is a risk of hypoglycemia. In the outpatient run-in period, this risk is expected to be less than the risk during
1063 the subjects' lives outside the trial based on data from earlier trials. All of our previous studies have shown that
1064 hypoglycemia is significantly reduced in all configurations of the bionic pancreas when compared with usual care.
1065 Based on our experience, we believe that the risk of hypoglycemia in the outpatient run-in period will be less
1066 than or equal to the risks that they are exposed to on a daily basis while living with type 1 diabetes outside of
1067 the trial. The exercise visit protocol is designed to cause hypoglycemia. Given frequent PG monitoring, protocols
1068 for treating hypoglycemia, and direct supervision by an RN or MD at all times, the risk of a hypoglycemic episode
1069 leading to significant harm to volunteers is expected to be very low. A small meal or snack will be made available
1070 to subjects after completion of the study.

1071

1072 Subjects may experience discomfort with insertion of the peripheral intravenous line, infusion sets, and Dexcom
1073 sensor into the subcutaneous tissues. The risk of discomfort due to insertion of infusion sets and Dexcom sensors

1074 may be greater than in their lives outside the trial because more infusion sets and sensors will be inserted than
1075 they may be used to.

1076

1077 There is a risk of risk of dizziness or lightheadedness from blood loss. However, typical blood loss will be limited
1078 to no more than 216 ml. Exclusion of subjects with anemia will help mitigate this risk.

1079

1080 There is a risk of headache, nausea, or vomiting in subjects due to the administration of exogenous glucagon.
1081 There is a possible risk of skin rash due to administration of exogenous glucagon. There may be risks of daily,
1082 low-level glucagon administration that have not become apparent during trials lasting up to 11 days. One
1083 possible risk is weight loss although no changes in weight have been observed in trials lasting up to 11 days.
1084 Others may include changes in blood chemistries or blood counts. The magnitude of the other possible risks due
1085 to daily administration of small amounts of glucagon are unknown, but are not expected to be high because
1086 mean glucagon levels have been in the normal fasted range in previous trials and there have be no other adverse
1087 events in previous bionic pancreas trials lasting up to 11 days. Of note, the incidence of nausea or vomiting has
1088 been low in prior studies and in one randomized double-blinded placebo controlled study it was not different
1089 from placebo.

1090

1091 **VIII. Potential Benefits**

1092

1093 Based on evidence from previous trials of the bionic pancreas and the design of this trial, subjects enrolled in the
1094 study may benefit from a reduction in risk of hypoglycemia and hyperglycemia and a better mean glucose during
1095 the outpatient run-in period.

1096

1097 Additionally, this study will help us to identify the utility of microdose glucagon in a bionic pancreas to prevent
1098 and treat hypoglycemia in the context of exercise, and FDA CDER has indicated that PG data demonstrating this
1099 will be required by in order to approve a bionic pancreas delivering glucagon on a chronic basis.

1100

1101 The data derived from this study will allow us to evaluate whether or not there is a relationship between
1102 volatile organic compounds in the breath and sweat and hypoglycemia. This information could be useful in
1103 developing noninvasive technologies to identify impending and actual hypoglycemia.

1104

1105 Subjects will be financially compensated for participating in the study.

1106

1107 **IX. Data and Safety Monitoring**

1108 **IX. a. Monitoring of Source Data**

1109

1110 During the experiment, Dexcom CGM data will be collected in various ways. Dexcom CGM data, calibration data,
1111 insulin dosing data, and glucagon dosing data will be automatically stored in the bionic pancreas device (from
1112 which it will be downloaded at intervals) and wirelessly streamed to the cloud where it will be stored to provide
1113 redundancy in data storage and mitigate the risk of data loss. All of the data will be combined in a single database
1114 that will be compared against the primary data files for integrity. The computer database will be backed up at
1115 least monthly and the backup media stored in a secure location.

1116

1117 Study staff will be encouraged to raise any concerns they may have or problems they have identified at any time.
1118 The PI, in consultation with the co-investigators, will decide a course of corrective action, and resolution or
1119 progress will be assessed no later than the next meeting.

1120

1121 An audit of procedures, regulatory documentation, and a sample of subject files will be performed by a member
1122 of the Diabetes Research Center at least biannually. The audit will be conducted by a staff member who is not
1123 directly involved in the conduct of the study. This audit will include a review of regulatory documentation, such

1124 as IRB and FDA correspondence, and a review of subject files, including a review of consents, case report forms,
1125 and other data from study visits.

1126
1127 A numeric code will be substituted for the subjects personal identifying information in the study database, which
1128 will be password protected. The key linking the medical record number of the subject with the numeric code,
1129 along with case report forms, and all information that is personally identifiable, will be kept in a locked filing
1130 cabinet in an investigator's locked office. All electronic records will be kept in a password protected computer
1131 database. All printed computer data will be disposed of confidentially when no longer needed. Only the study
1132 staff will have access to the study database. Subjects may not withdraw from the de-identified database, but
1133 they may elect to have the key linking their medical record to the de-identified database destroyed.

1134
1135 The study data may be shared with collaborators at Boston University and at the MITRE Corporation (a non-profit
1136 research corporation), but only in a form in which all personally identifiable information has been removed (e.g.
1137 combined database including BG values, record of insulin and glucagon delivered by the device, and blood insulin
1138 and glucagon levels). Shared data will be in the form of a database in which only a number identifies subjects.

1139
1140 Subjects may not withdraw their data, as it will be stored in non-personally identifiable form.

1141
1142 **IX. b. Safety Monitoring**

1143
1144 This study is considered moderate risk. An external Data and Safety Monitoring Board will oversee the conduct
1145 of the study and review its results on a regular basis. Additionally, the DSMB will be informed in the event of any
1146 severe or unexpected adverse events. The DSMB will be informed if there are any changes to the study protocol
1147 that could significantly impact the safety or scientific validity of the study. A final DSMB meeting will convene
1148 after the completion of the study. Safety and efficacy data will also be reported to the FDA in compliance with
1149 applicable regulations.

1150
1151 The participation of individual subjects will be discontinued if they experience:

- 1152
- 1153 • Diabetic ketoacidosis requiring hospitalization
 - 1154 • Seizure or unconsciousness associated with hypoglycemia
 - 1155 • Persistent nausea and vomiting thought to be related to glucagon dosing

1156 If more than 2 subjects must be withdrawn from the study for these reasons, the study will stop and a vote of
1157 the DSMB will be required to restart it. All serious and unexpected events will be reported to the DSMB within
1158 72 hours.

1159 Note that subjects may discontinue participation at any time and subjects may be removed from the trial for
1160 other reasons, for instance failure to comply with study procedures or concurrent illness that is unrelated to the
1161 bionic pancreas but that precludes safe participation. Discontinuation of participation for these reasons will not
1162 contribute to a decision to discontinue the trial.

1163
1164 **IX. c. Adverse Event Reporting Guidelines**

1165
1166 An adverse event (AE) is any untoward medical occurrence in a patient or clinical investigation subject
1167 administered/using product and which does not necessarily have to have a causal relationship with this
1168 treatment. An Adverse Event can therefore be any unfavorable and unintended sign (including an abnormal
1169 laboratory finding), symptom, or disease temporally associated with the use of a product, whether considered
1170 related to the product or not.

1171

1172 A serious adverse event (SAE) is an experience that at any dose results in any of the following: (death, life-
1173 threatening experience, inpatient hospitalization or prolongation of existing hospitalization, a persistent or
1174 significant disability/incapacity or is a congenital anomaly/birth defect. Important medical events that may not
1175 result in death, be life-threatening, or require Hospitalization may be considered a serious adverse event when,
1176 based upon appropriate medical judgement, they may jeopardize the patient or subject or require medical or
1177 surgical intervention to prevent one of the outcomes listed in this definition. Suspicion of transmission of
1178 infectious agents must always be considered an SAE.

1179
1180 Serious adverse reaction (SAR) is an adverse event that fulfils both the criteria for a serious adverse event and
1181 the criteria for an adverse reaction.

1182
1183 Whether adverse events are expected or unexpected will be base on product labeling for the insulins and
1184 glucagon used in the study, the expected functioning of the bionic pancreas, and the potential risks described in
1185 the consent document.

1186
1187 The causality of each AE should be assessed by the Investigator per the following classification:

- 1188 • Probable: Good reason and sufficient documentation to assume a causal relationship
- 1189 • Possible: A causal relationship is conceivable and cannot be dismissed
- 1190 • Unlikely: The event is most likely related to etiology other than the trial product

1191
1192 The PI and co-investigators will review any adverse events after each experiment. Any serious or unexpected but
1193 possibly related adverse events will be communicated to the PI as soon as possible and within 48 hours of the
1194 time they are detected. Adverse events will be reported promptly to the Partner's IRB and to the BU IRB.
1195 Collaborator [name] is the sponsor of the Investigational Device Exception (IDE) for the bionic pancreas to
1196 be used in this trial. Reports of adverse events will be made to the FDA in compliance with the terms of IDE.

1197 The Investigator will forward all serious adverse events (SARs) and reports on pregnancy during the use of Novo
1198 Nordisk product to Novo Nordisk. These safety reports must be sent to Novo Nordisk within 15 calendar days
1199 from the investigator's first knowledge of the event. In addition to SARs, any other events that have been
1200 submitted to the IRB must be sent to Novo Nordisk at the time of submission.

1201
1202 AE information should include the following:

- 1203 • Study name
- 1204 • Patient identification (i.e. subject number, initials, sex, age)
- 1205 • Event (diagnosis)
- 1206 • Trial drug
- 1207 • Reporter
- 1208 • Causality
- 1209 • Outcome

1210 1211 **X. Subject Compensation**

1212
1213 Financial compensation will be provided to all subjects who complete the screening visit. Subjects will be paid
1214 \$25 for completing the screening visit whether or not they are eligible to participate in the study. Study
1215 participants will be compensated \$50 for completing each study visit. Thus the total compensation for a subject
1216 who completed the study could be up to \$225. Parking expenses will be paid for up to \$30 per subject. Subjects
1217 who are unable to complete the study or chose to stop participation will receive prorated compensation for the
1218 portion of the study visits that they complete.

1219 1220 **XI. Publication Plans**

1221

1222 The data derived from this study will be published in a peer-reviewed journal. Candidate journals include:
1223 Diabetes Care; Diabetes; Diabetologia; Diabetes, Obesity and Metabolism; and Journal of Clinical Endocrinology
1224 and Metabolism.

1225

1227

1228

1229

1230

1231

1232

1233

1234

1235

1236

1237

1238

1239

1240

1241

1242

1243

1244

1245

1246

1247

1248

1249

1250

1251

1252

1253

1254

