185 wearing the bionic pancreas while they exercised to see if it is possible to identify a volatile organic compounds
186 (VOC) marker for hypoglycemia. These participants wore the bionic pancreas for 4 days as an outpatient run-in
187 to their fasted exercise visit. Some of the subjects were tested multiple times during up to three rounds of
188 testing. This provided sets of clinical samples from 79 exercise sessions. The breath samples have been
189 analyzed by a research team at the MITRE Corporation (a non-profit research corporation) to identify and
190 measure the VOCs present, as well as how their concentrations vary relative to the blood glucose of the
191 participants. The variations in the concentrations of several VOCs in the breath of diabetics appeared to
192 correlate with variations in the blood glucose concentration. However, in experiments performed thus far only
193 two participants developed hypoglycemia due to the efficacy of the BP and the circumstances of the exercise
194 testing. Therefore, more data needs to be collected to allow demonstration of a statistically significant
195 correlation between a VOC breath signature and hypoglycemia. Further clinical testing is necessary to examine
196 the relationship between breath and sweat VOCs and hypoglycemia.
197

198 **I. d. Rationale and Potential Benefits**

199 We will compare the ability of the bi-hormonal bionic pancreas and the insulin only bionic pancreas to prevent
200 and treat exercise induced hypoglycemia. In this study we have modified the circumstances and type of exercise
201 in ways that we believe will increase our ability to detect differences between the insulin-only and bihormonal
202 bionic pancreas systems. In this study the bionic pancreas will adapt to the individual in a bihormonal
203 configuration at the lowest glucose target we have previously shown to be safe (100 mg/dl) and then either
204 remain in the bihormonal configuration for exercise or be switched to the insulin-only configuration just before
205 exercise at the same glucose target. In the previous study the lowest glucose target used was 110 mg/dl, which
206 likely reduced the incidence of hypoglycemia in the insulin-only configuration. It will be safe to test the insulin-
207 only configuration at this glucose target because it will only be used while participants are under direct
208 monitoring in the Diabetes Research Center (DRC). We will also have participants stay overnight in a hotel near

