209 the DRC the night before the exercise visits because we suspect the stress of commuting to the DRC through
210 Boston traffic may have elevated the pre-exercise plasma glucose values in many participants, thereby making it
211 more difficult to observe hypoglycemia during exercise. Finally, we have changed the type of exercise from
212 cycling at a moderate pace with a heart rate of 120-140 beats per minute, to a mild exercise (walking on a
213 treadmill at a comfortable pace) for a longer period of time (up to 1 hour). It is well known that more intense or
214 unaccustomed exercise can often result in elevations rather than reductions in plasma glucose due to release of
215 stress hormones. Therefore, we have chosen a more mild exercise that all participants will be comfortable with
216 and have increased the duration to maximize the chance that hypoglycemia may occur in the insulin-only
217 configuration of the bionic pancreas.
218

219 In this setting we will again measure volatile organic compounds in breath and sweat of participants with type 1
220 diabetes with normoglycemia and exercise induced hypoglycemia to determine if there is a relationship
221 between VOC signature and hypoglycemia. If no hypoglycemia is induced by exercise then after a recovery
222 period we will administer a small insulin dose to increase the likelihood of achieving mild hypoglycemia and
223 thereby increase the number of breath and sweat samples collected under hypoglycemic conditions. This will
224 be done only if hypoglycemia did not occur during exercise or in the recovery period afterwards so this
225 additional intervention will not interfere with interpretation of the results of the exercise study.
226

227 **II. Hypothesis and Specific Aims**

228 We hypothesize that the bi-hormonal bionic pancreas will reduce the amount of hypoglycemia experienced
229 during and after exercise relative to an insulin-only configuration of the bionic pancreas. We hypothesize that by
230 collecting the breath and sweat of type 1 diabetics while they are in normoglycemic and hypoglycemic states,
231 and comparing the profile of volatile organic compounds in both between these two states, we will be able to
232 determine a relationship between volatile organic compounds in breath and sweat and hypoglycemia.
233

234 **Aim 1.** To evaluate the incremental utility of glucagon in the context of automated insulin delivery by the bionic

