- 266 • Live within 120 minute radius of Massachusetts General Hospital
- 267 • Willing to remain within a 250 mile radius of the central monitoring location during the outpatient run-
268 in period. No air travel will be allowed, and subjects will still be expected to follow the visit schedule as
269 described.
- 270 • Willing to spend the night prior to both exercise visits in a hotel and fast overnight prior to exercise
- 271 • Willing and able to avoid deodorant, scented lotions, and scented laundry detergent on your clothes on
272 the days of the exercise visits
- 273 • Willing to wear two steel cannula infusion sets (6 mm Contact Detach) and one Dexcom CGM sensor and
274 change sets frequently (a new glucagon infusion set daily and a new insulin infusion set every other day
275 during the outpatient run-in period)
- 276 • Have a mobile phone they will have access to at all times during the outpatient run-in period for making
277 contact with study staff

278
279 No subjects will be excluded on the basis of gender or race. The requirement that subjects manage their diabetes
280 using subcutaneous insulin infusion pump therapy is imposed because multiple daily injection therapy involves
281 the use of long-acting basal insulin that would require an extended washout period.
282

283 **III. b. Exclusion Criteria**

- 284 • Unable to provide informed consent (e.g. impaired cognition or judgment)
- 285 • Unable to safely comply with study procedures and reporting requirements (e.g. impairment of vision or
- 286 dexterity that prevents safe operation of the bionic pancreas, impaired memory, unable to speak and
- 287 read English)
- 288 • Current participation in another diabetes-related clinical trial that, in the judgment of the principal
- 289 investigator, will compromise the results of this study or the safety of the subject
- 290 • Pregnancy (positive urine HCG), breast feeding, plan to become pregnant in the immediate future, or
- 291 sexually active without use of contraception
- 292 ○ Subjects must use acceptable contraception for the two weeks prior to the study, throughout the
- 293 study and for the two weeks following the study.
- 294 ○ Acceptable contraception methods include:
- 295 ▪ Oral contraceptive pill (OCP)
- 296 ▪ Intrauterine Device (IUD, hormonal or copper)
- 297 ▪ Male condoms
- 298 ▪ Female condoms
- 299 ▪ Diaphragm or cervical cap with spermicide
- 300 ▪ Contraceptive patch (such as OrthoEvra)

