742 be filled with two vials of freshly reconstituted GlucaGen vials (Novo Nordisk). The glucagon infusion set
743 will be changed daily with the reservoir change. We have received an IND exemption from the FDA for
744 use of glucagon in this application for up to 27 hours. The insulin reservoir will be changed every other
745 day during the outpatient run-in period.
 - 746 • On days when both the insulin and glucagon reservoirs will be changed, subjects will be asked to change
747 them at different times in the day, separated by at least one hour. They will label the infusion sets and
748 tubing with supplied labels to avoid confusion or cross connection.

749
750 **Exercise Visits:**

- 751 • Subjects will have the option of completing the exercise visit at least 24 hours and up to 96 hours after
752 completing Visit 1
- 753 • Subjects will arrive to the exercise visit having fasted since 12:00 AM the night before (treatment with
754 simple carbohydrates of up to 30 grams for a low blood sugar is allowed). If the patient is not fasted,
755 the visit will be rescheduled. Subjects will sleep in a local hotel the night before the exercise visit to
756 eliminate the effects of their morning routine and the commute to the Diabetes Research Center on
757 their glycemic control.
- 758 • A plasma glucose will be checked via fingerstick using the Statstrip Xpress upon arrival. If PG is ≥ 150
759 mg/dL, the subject will either wait for the PG to fall below 150 mg/dL or the visit will be rescheduled. If
760 PG is <50 mg/dL, the patient will be treated with simple carbohydrates according to the 15/15 rule (15
761 grams of carbohydrates, repeated in 15 minutes if necessary).
- 762 • We will ask subjects to avoid certain skin care products that will interfere with sweat sample collection
763 on the day of the visit.
- 764 • Study staff will fill the tandem t:slim glucagon pump with either glucagon or placebo (normal saline)
765 according to the subject's randomization order. The subject will not be aware of their randomization.
766 New infusion sets for both the glucagon/placebo and insulin pumps will be placed using an FDA approved
767 steel cannula infusion set.
- 768 • The body weight of the subject will be documented.
- 769 • A 20 gauge or smaller peripheral I.V. will be placed.
- 770 • Subjects will walk on a treadmill which is intended to induce hypoglycemia. Subjects will not be allowed

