771 to move faster than a comfortable walking pace. Subjects will be reminded that the goal is not to raise

772 their heart rate or sweat, but to keep moving and keep their leg and core muscles activated without
773 excessive exertion.

774 • Subjects will continue walking until the hypoglycemia threshold has been reached, or up to 1 hour.
775 Exercise will be terminated when:

- 776 ○ Subjects reach a PG of 50 mg/dl or lower
- 777 ○ Subjects reach a PG of < 60 mg/dl but > 50 mg/dl for three consecutive measurements taken
778 every 5 minutes and thereafter choose to treat with oral carbohydrates (subjects may elect not
779 to treat hypoglycemia with carbohydrates if the PG is >50 mg/dl)
- 780 ○ They have completed 1 hour of walking with no treatment for hypoglycemia

781 • During exercise, BG measurements using the YSI will be obtained according to the following protocol:

- 782 ○ If PG is ≥ 80 mg/dl, BG measurements will be obtained off of the IV line every 10 minutes
- 783 ○ If the PG is < 80 mg/dl, BG measurements will be obtained off of the IV line every 5 minutes.
- 784 ○ If PG is <60 mg/dL for more than three consecutive measurements but is still > 50 mg/dl, subjects
785 will have the option to treat with carbohydrates, and if subjects choose to treat exercise will be
786 terminated.
- 787 ○ If PG is < 50 mg/dL, exercise will be terminated and subjects will be required to treat with
788 carbohydrates.
 - 789 ▪ Carbohydrates will be given according to the following protocol: Dextrose (g) = BSA
790 (m^2)/[1.7 m^2 (women) or 1.9 m^2 (men)] *15g
 - 791 ▪ Repeat treatments will be given at 15 minute intervals as long as hypoglycemia continues
- 792 ○ If the YSI fails, the Nova StatStrip Xpress meter will be used for glucose measurements.

793 • Study staff will collect samples of sweat from the subject's underarm and will ask subjects to exhale into
794 a breath collection device at the beginning of, at intervals during, and at the completion of exercise, with
795 increased frequency during any episodes of hypoglycemia. These samples will be collected, de-identified
796 and shipped out to collaborators at the MITRE Corporation for analysis of the relationship between
797 volatile organic compounds in breath and sweat and hypoglycemia.

798 • PG monitoring off of the IV line will continue after the exercise is completed or stopped according to the
799 following protocol:

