- 944 • Time from the start of exercise to first PG < 60 mg/dl, if found

945

946 **VI. b. 3. Other endpoint analyses**

947

948 **Exercise and post-exercise monitoring period**

- 949 • Plasma glucose at the start of exercise
- 950 • Mean slope of the CGM glucose curve in the 30 minutes prior to the start of exercise
- 951 • Area over the plasma glucose curve and <60 mg/dl accumulated at the time the participant requests
- 952 carbohydrate treatment or treatment is required by protocol during exercise visit
- 953 • Duration with CGM glucose <60 mg/dl during exercise visit
- 954 • Nadir CGM glucose during exercise visit
- 955 • Area over the plasma glucose curve and <60 mg/dl during exercise visit, calculated by CGM
- 956 • Time from the start of exercise to first CGM reading < 60 mg/dl

- 957 • Total glucagon dosing by bi-hormonal bionic pancreas from the start of exercise until the end of the
958 exercise and post-exercise monitoring period
- 959 • Grams of oral carbohydrates given to the subject to treat hypoglycemia during the exercise and post-
960 exercise monitoring period
- 961 • Total glucagon dosing by bi-hormonal bionic pancreas from the start of exercise until the end of the visit
- 962 • **VOC outcomes**
- 963 • Identification of volatile and organic compound or compounds in breath and sweat that correlate(s)
964 with hypoglycemia
- 965 • Identification of volatile organic compounds in breath and sweat that correlate with normoglycemia
966 and/or hyperglycemia
- 967
- 968

969 **Outpatient period**

- 970 • **CGM-based outcomes**
- 971 • Mean CGM glucose – 24-hours, daytime (7:00 AM – 11:00 PM), and nighttime (11:00 PM – 7:00 AM)
- 972 • Time in the following ranges – 24-hours, daytime (7:00 AM – 11:00 PM), and nighttime (11:00 PM –
973 7:00 AM):
- 974 ○ <70 mg/dl
- 975 ○ <60 mg/dl
- 976 ○ <54 mg/dl
- 977 ○ <50 mg/dl
- 978 ○ 70-180 mg/dl
- 979 ○ 70-120 mg/dl
- 980 ○ 70-140 mg/dl
- 981 ○ >180 mg/dl
- 982 ○ >250 mg/dl
- 983 • Percentage of participants achieving a mean CGM glucose of ≤ 154 mg/dl
- 984 • Correlation between mean Dexcom CGMG and mean number of meal announcements per day
- 985 • CGM MARD from Dexcom G5 CGM versus time-stamped BG values from meter downloads (any other
986 BG values will not be considered)
- 987 • CGM Reliability index, calculated as percent of possible values actually recorded by CGM
- 988 • **PG-based outcomes**

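### The rules against outside volatiles cover skin and clothing only, although breath is also sampled; oral and inhaled products are neither limited nor recorded (minor)

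*Combined protocol and SAP*

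**What the plan says.** All references are to the combined protocol and SAP.

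- **Avoidance rules.** Section III.a requires participants to be "Willing and able to avoid deodorant, scented lotions, and scented laundry detergent on your clothes on" the days of the exercise visits and gives no reason. Section V.d.v (Exercise Visits) adds: "We will ask subjects to avoid certain skin care products that will interfere with sweat sample collection". That second rule is the only one with a stated purpose, and the purpose is sweat.
- **Breath sampling.** In V.d.v participants exhale into "a breath collection device at the beginning of, at intervals during, and at the completion of exercise", more often during hypoglycemia. Aim 2 in section II has breath and sweat taken at intervals through the whole visit.
- **Earlier signal.** Section I.c reports on breath: "The variations in the concentrations of several VOCs in the breath of diabetics appeared to" follow blood glucose.
- **Other restrictions.** V.d.v: "Subjects will arrive to the exercise visit having fasted since 12:00 AM the night before". Section V.d.iii bars recreational drugs apart from alcohol and does not name tobacco.
- **Analysis.** Section II rests the VOC hypothesis on collecting samples in the two glucose states "and comparing the profile of volatile organic compounds in both between these two states, we will be able to" establish a relationship. VI.b.3 lists, among the other endpoints, compounds tied to hypoglycemia and, separately, compounds tied to normoglycemia or hyperglycemia. It states no model, reporting threshold or time term.
- **Expected yield.** VI.c gives no formal power for Aim 2. It expects at least 30 visits with hypoglycemia, with normoglycemic comparison samples from both before and after the episode on the same day.

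**The concern.** The plan accepts that outside volatiles can spoil samples, but guards only against those carried on skin and clothes. Breath, which gave the only earlier correlation reported, is open to residues of tobacco, vaping, mouthwash and toothpaste. Participants wake in a hotel near the center, so brushing teeth shortly before arrival is to be expected.

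Such residues are not spread evenly over the two glucose states. The first set is taken as exercise begins, and hypoglycemia is induced afterwards. A compound that falls with time since exposure will tend to be lower in a hypoglycemic set than in the set before it, with no link to glucose. Residues also add noise that can hide a real marker. VOC identification serves one of the two stated aims, and exposure that was never recorded cannot be adjusted for later.

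**Working it through.** The plan gives no figure on this point to reproduce. The check has four parts.

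**1. Coverage of the rules**

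| Source of volatiles | Skin and clothing rules | Midnight fast | Drug policy |
|---|---|---|---|
| Deodorant, lotion, detergent | covered | – | – |
| Food | – | covered | – |
| Gum, mints | – | arguably covered | – |
| Tobacco, vaping | – | – | not named |
| Mouthwash, toothpaste | – | – | – |

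Social history is collected (V.a, VI.a.1), but only as it bears on eligibility. No criterion concerns smoking, so smoking status need not be captured.

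**2. Link between glucose state and elapsed time**

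VI.c assumes rates of 25% and 75%: 0.25 × 20 + 0.75 × 20 = 5 + 15 = 20 visits with exercise-related hypoglycemia. At least 30 are expected in all, so roughly 30 − 20 = 10 would follow the correction bolus. With a full hour of walking and 30 minutes of monitoring, that bolus comes about 60 + 30 = 90 minutes after exercise starts. Hypoglycemic sets are thus later than the first set, by varying amounts.

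**3. Sign-test illustration (exposure is assumed)**

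Take 20 subjects, of whom e carry the same fading compound and all change in one direction; the other 20 − e split evenly. Then x = e + (20 − e)/2, and the two-sided exact p = 2 × Σ C(20,k)/2^20 for k from x to 20, with 2^20 = 1,048,576.

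| e | x of 20 | Calculation | p |
|---|---|---|---|
| 4 | 12 | 2 × 263,950 / 1,048,576 | 0.50 |
| 8 | 14 | 2 × 60,460 / 1,048,576 | 0.115 |
| 12 | 16 | 2 × 6,196 / 1,048,576 | 0.012 |
| 16 | 18 | 2 × 211 / 1,048,576 | 0.0004 |

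This compares hypoglycemia only with earlier samples. The documents give no value for e.

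**4. Effect of the after-hypoglycemia samples (simulation on assumptions)**

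Assumed: 30 visits treated as independent, all carrying a compound unrelated to glucose. Its level is A × 2^(−t/h), with t in minutes from the first sample and A lognormal (log SD 0.5). Sampling is at 0 and 20 minutes (before), 45 and 55 (hypoglycemia), and 80 and 110 (after). Noise SD is 0.3 or 0.6 of the typical starting level. The test is a paired t-test at 0.05, with 4,000 runs.

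Expected difference at h = 30, as a fraction of the starting level:
- hypoglycemia mean: (0.3536 + 0.2806)/2 = 0.3171
- against before only: 0.3171 − (1 + 0.6300)/2 = −0.498
- against before and after: 0.3171 − (1 + 0.6300 + 0.1575 + 0.0787)/4 = −0.149

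| Half-life h (min) | Difference, before only | Difference, before and after | False positives, before only | False positives, before and after |
|---|---|---|---|---|
| 15 | −0.597 | −0.255 | 100% | 80–100% |
| 30 | −0.498 | −0.149 | 100% | 39–91% |
| 60 | −0.335 | −0.056 | 90–100% | 11–25% |
| 120 | −0.196 | −0.013 | 49–95% | 5–6% |
| 240 | −0.106 | −0.001 | 18–55% | about 5% |

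Each range runs from the higher to the lower noise level. Because every visit is taken as exposed, these rates are at the high end. All differences are negative: the compound is lower in hypoglycemia.

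**The case against.** The strongest reply is that the design already contains most of the remedy. VI.c plans normoglycemic samples after hypoglycemia as well as before, and a steadily fading compound is lowest in those later sets. Under the assumptions above, that brings the false-positive rate to about nominal at half-lives of 120 minutes or more. Residues that fade fast enough to survive this correction also lose most before the first sample: V.d.v places an arrival fingerstick, possible waiting, pump filling, new infusion sets, weighing and IV placement before exercise. For scale, 60 minutes leaves (1/2)^4 = 6% of a residue with a 15-minute half-life, though the documents give no set-up time. This largely stands, and it is why the point is minor. It is not a full cure. The sampling list in V.d.v ends at the completion of exercise, so the after-sets rest on the expectation in VI.c and the wording of Aim 2. They may also follow oral carbohydrate, a new oral exposure.

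Three further replies have weight. Drift with time affects any compound that changes with exercise or fasting, so an avoidance rule alone would leave that confounding in place. VOC identification is listed under other endpoints and did not set the sample size. Consent pages are not in the copy reviewed, and an instruction on breath may stand there. These lower the priority and the certainty; they do not supply the missing protocol instruction.

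A reader might infer that a residue would be named as a compound that rises in hypoglycemia. The documents do not support that: a fading residue would be lower, and so would appear as an inverse marker or under the separate normoglycemia endpoint. Nor can one say that residues are systematically higher in all normoglycemic sets, since the after-sets are normoglycemic too. Nor is it shown that both avoidance rules exist for sweat alone; only the V.d.v rule says so.

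**Conclusion.** The gap is real and small. On the text reviewed, outside volatiles are restricted on skin and clothing only, breath is sampled as well, and tobacco, vaping, mouthwash and toothpaste are neither limited nor recorded.

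The possible harm is a spurious inverse or normoglycemia-linked compound, plus added noise. It matters mainly for residues with half-lives of up to about an hour during sampling, and only if many participants share the exposure. In the sign-test illustration nothing reaches 0.05 with 4 or 8 of 20 exposed, and 12 or 16 do, before any credit for the after-samples. Exposure, half-lives, sampling times and noise are all assumptions, and the plan sets no threshold for reporting a compound, so no single false-positive rate can be claimed.

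It would be wrong to carry this over to the glucagon comparison. The primary and secondary endpoints are plasma glucose measures and are unaffected. Severity: optional, minor.

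**What to change.** 1. Extend the instructions in III.a and V.d.v to breath: no tobacco, vaping, mouthwash, scented toothpaste, gum or mints on the morning of each exercise visit until sampling ends, with a water rinse allowed. The rules for treating hypoglycemia stay as they are.
2. Add a checklist item at arrival for compliance, smoking status and time of last oral care.
3. In the VOC analysis, use both the before and the after normoglycemic sets and include elapsed time as a covariate. State in V.d.v that after-hypoglycemia sets are collected, in line with VI.c.
4. Use visits without hypoglycemia only as a supporting time reference. With at least 30 of 20 × 2 = 40 visits expected to include hypoglycemia, at most about 10 remain.

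The cost is one instruction line, one checklist item and one model term. The downside is minor inconvenience for participants, including morning abstinence for smokers. Dosing and visit timing do not change.
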